An Open-label Phase Ib/II Study of Avelumab in Combination with 5-azacytidine (Vidaza) for the Treatment of Patients with Refractory/Relapsed Acute Myeloid Leukemia
2016-0444

Core Protocol Information

Short Title	Avelumab (antiPDL1) and azacytidine in AML
Study Chair:	[name]
Additional Contact:	[name] [name] Leukemia Protocol Review Group
Additional Memo Recipients:	Recipients List OPR Recipients (for OPR use only) None Study Staff Recipients None
Department:	Leukemia
[contact]
Unit:	428
Study Manager:	[name]
Full Title:	An Open-label Phase Ib/II Study of Avelumab in Combination with 5-azacytidine (Vidaza) for the Treatment of Patients with Refractory/Relapsed Acute Myeloid Leukemia
Public Description:	N/a
Protocol Type:	Standard Protocol
Protocol Phase:	Phase I/Phase II
Version Status:	Terminated 10/03/2019
Version:	15
Document Status:	Saved as "Final"
Submitted by:	[name]--8/13/2019 10:24:00 AM
OPR Action:	Accepted by: [name] -- 8/22/2019 9:13:02 AM

Which Committee will review this protocol?

- The Clinical Research Committee - (CRC)

Avelumab and 5_azacytidine in AML_IST_(Final) 7.27.2018.doc

Protocol Body

An Open-label Phase Ib/II Study of Avelumab in
Combination with 5-azacytidine (Vidaza) for the Treatment
of Patients with Refractory/ Relapsed Acute Myeloid
Leukemia

Principal Investigator: [name].

Co-PI: [name], M.D.

Sponsor: University of Texas, MD Anderson Cancer Center

IND number: 131967

University of Texas

MD Anderson Cancer Center

Leukemia Department, Unit

1.1 **OBJECTIVES**

1.2 **Primary Objectives**

Part a. Phase IB

To determine the maximum tolerated dose (MTD) and dose limiting toxicity (DLT) of avelumab in combination with 5-azacytidine in patients with refractory/ relapsed acute myeloid leukemia (AML).

Part b. Phase II

To determine the overall response rate (ORR) defined as complete remission (CR/complete remission with incomplete platelet recovery (CRp)/complete remission with incomplete count recovery (CRi)/partial remission (PR)/hematologic improvement (HI)/morphologic leukemia free state (MLFS) of avelumab in combination with 5-azacytidine in patients with refractory/ relapsed AML.

1.3 **Secondary Objectives:**

1. To determine the number of patients who achieve > 50% reduction in blasts on therapy with this combination.
2. To determine the duration of response, disease-free survival (DFS), and overall survival
3. (OS) of patients with refractory/ relapsed AML treated with this combination.

1.4 **Exploratory Objectives:**

1. To study immunological and molecular features at baseline and at predefined time-points on-therapy with avelumab and azacytidine in the peripheral blood and bone marrow to include (a) quantify immune ligand expression by the AML blasts and AML stromal components (MDSCs and MSCs) including 4-1BBL, ICOSL, PD-L1, PD-L2, OX-40L, CD137L and (b) determine the quantitative expression of positive and negative co-stimulatory molecules on individual T-lymphocyte subsets including 4-1BB, CTLA-4, ICOS, PD-1, OX40, LAG-3 and TIM-3, and (c) identify the immunophenotype of tumor-infiltrating T-lymphocytes (TILs) pre- and post-therapy with the combination: CD8+, CD4+ effector, or CD4+ regulatory.
2. To develop a micro-array based gene expression profile (GEP) predictor of response to anti-PDL1 and epigenetic therapy in AML.
3. To determine the correlation of responses to the combination with baseline cytogenetic and molecular abnormalities.

2.1 **BACKGROUND**

2.1.1 **Acute myeloid leukemia**

Approximately, 30-40% of adults with AML fail to achieve CR with 1 or 2 cycles of induction chemotherapy, and are deemed primary refractory. The outcomes of patients with acute myeloid leukemia (AML) who are refractory to induction therapy are dismal, with low

response rates to salvage chemotherapy and poor long-term survival¹⁻³. We have previously reported a dismal median OS of 3.8 months for patients with AML who are refractory to HiDAC-containing induction therapy (defined as $\geq 1\text{gm/m}^2$ cytarabine per dose)². Salvage therapy in such patient populations yielded a response rate of 18% and median response duration of 9 months.

These results emphasize the need to explore alternate salvage regimens for patients with relapsed/refractory AML. The development of novel and effective anti-AML agents and/or combinations is crucial to improving the outcome of AML.

2.1.2 Relapsed/Refractory AML:

Therapy for AML has improved only modestly over the last 4 decades. Traditional induction chemotherapy produces cure rates of 30% in adults with AML⁴⁻⁶. Patients with relapsed AML have an overall survival of 1 to 4 months with current salvage therapy^{2,7}. We have previously reported a dismal median OS of 3.8 months for patients with AML who are refractory to HiDAC-containing induction therapy (defined as $\geq 1\text{gm/m}^2$ cytarabine per dose). Salvage therapy in such patient populations yielded a response rate of 18% and median OS of 4.5 months. The preliminary data from investigators in our group⁸ and from others^{9,10} suggest that immune therapies may be a crucial third modality in combination with cytotoxic and/or targeted molecular therapy to produce deeper and/or more durable responses in AML and MDS.

These results emphasize the need to explore alternate salvage regimens for patients with relapsed/refractory AML. The development of novel and effective anti-AML agents and/or combinations is crucial to improving the outcome of AML.

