- 4.2.7 Patients who are <90 days post allogeneic stem cell transplant will be excluded. Patients beyond 90 days post-allogeneic stem cell transplant with uncontrolled active GVHD > grade 1 will be excluded. Patients who are on a stable dose of immunosuppressive therapy (tacrolimus, cyclosporine, or other) for > 2 weeks will be eligible but those with recent increase in the immunosuppressive medication dose within last 2 weeks to control GVHD will not be included. Note: Subjects may be using systemic corticosteroids or topical or inhaled corticosteroids post allogeneic stem cell transplant (inclusion based on post stem cell transplant activity and tolerability of checkpoint inhibitor by Matthew D, et al., ASH 2015 Annual Conference abstract # 860). Patients requiring ≥ 1 mg/kg prednisone for GVHD management at the time of screening will not be eligible until the prednisone can be weaned to <1 mg/kg. Such patients should be monitored for at least 14 days and if no flare of GVHD requiring re-escalation of steroids or additional interventions for the GVHD they will be eligible.
- 4.2.8 Patients with symptomatic CNS leukemia or patients with poorly controlled CNS leukemia.
- 4.2.9 Active and uncontrolled disease/(active uncontrolled infection, uncontrolled hypertension despite adequate medical therapy, active and uncontrolled congestive heart failure NYHA class III/IV, clinically significant and uncontrolled arrhythmia) as judged by the treating physician.
- 4.2.10 Patients with known Human Immunodeficiency Virus seropositivity will be excluded.
- 4.2.11 Known to be positive for hepatitis B by surface antigen expression. Known to have active hepatitis C infection (positive by polymerase chain reaction or on antiviral therapy for hepatitis C within the last 6 months)
- 4.2.12 Any other medical, psychological, or social condition that may interfere with study participation or compliance, or compromise patient safety in the opinion of the investigator
- 4.2.13 All other significant diseases (for example, inflammatory bowel disease, uncontrolled asthma), which, in the opinion of the Investigator, might impair the subject's tolerance of trial treatment
- 4.2.14 Patients unwilling or unable to comply with the protocol.

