Since the effect of both avelumab and 5-azacytidine may be delayed, patients with high WBC counts may receive hydroxyurea prior to study entry. Hydroxyurea is allowed before the start of study therapy and during the study treatment. Hydroxyurea use would be recorded in the case report form (CRF). Concurrent therapy for CNS prophylaxis or continuation of therapy for controlled CNS disease is permitted. With the exception of these agents, concomitant systemic chemotherapy or radiation therapy is not permitted. Subjects are not allowed to participate concurrently in any other therapeutic clinical study.

Subjects may be receiving systemic corticosteroids (daily doses ≤ 10 mg of prednisone or equivalent if indicated for adrenal replacement or antiemetic therapy), topical, or inhaled corticosteroids at study enrollment. They may receive systemic, topical, inhaled, or enteric corticosteroids while on study without limitation if they develop conditions that require corticosteroid therapy; such subjects are not required to discontinue study participation.

All ongoing medications and therapies (including herbal products, nutritional supplements, and nontraditional medications) at screening will be considered prior medications. Concomitant medication data will not be collected or entered into the case report form other than hydroxyurea as mentioned above; however, the subject's medication record will contain a list of concomitant medications. If a prohibited medication is inadvertently administered/ taken by the patient, the patient may remain on study as long as the prohibited medication is discontinued as soon as feasible. If a prohibited medication is considered essential for the patient well being, continuation on study with concomitant administration of such medication(s) will need to be discussed with and approved by the principal investigator and medical monitor

Table 4: Instructions for the use of concomitant medications and therapies

Category of Use	Medication	Comment on Use	Restriction on Use
Recommended	Prophylactic antibiotics, antifungal agents, and antiviral agents	Strongly encouraged	None
	Antiemetic agents	According to standard of care at MDACC	None
Allowed	Oral allopurinol or rasburicase	At investigators discretion	None
	Leukapheresis	According to standard of care at MDACC	Before induction 1 day 1 only
	Red blood cell	None	None

Category of Use	Medication	Comment on Use	Restriction on Use
	transfusion		
	Platelet transfusion	None	None

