7.1.6 Pretreatment optional correlative studies (see below)

7.1.7 Electrocardiogram (EKG)

7.1.8 Routine urinalysis

7.1.9 Chest X-ray

7.1.10 TSH, free T3, free T4, free & total cortisol

7.1.11 Respiratory PCR panel

7.2 Evaluation During Treatment

7.2.1 Physical exam at the start of each cycle (± 4 days) and documentation of all concomitant medications.

7.2.2 CBC, platelet count, differential twice weekly (± 4 days) for the first 3 cycles, then every 2-4 weeks (differential can be omitted if WBC is $\leq 0.5 \times 10^9/L$)

7.2.3 Creatinine, total bilirubin, ALT, or AST, calcium, magnesium, glucose, BUN, uric acid, fractionated bilirubin, alkaline phosphatase, sodium, potassium, chloride, bicarbonate twice weekly (± 4 days) for the first 3 cycles, then every 2-4 weeks.

7.2.4 TSH, free T3, free T4, and free & total cortisol once monthly (± 4 days) for the first 3 cycles, then every 3 months (± 4 days).

7.2.5 Bone marrow aspiration on day 28 (± 7 days), then every 1-4 cycles. Bone marrow tests can be ordered more frequently if mandated by development of peripheral blood counts. No repeat bone marrow is necessary if nonresponse or progressive disease can be unequivocally diagnosed from peripheral blood tests or, in patients with a WBC < 0.3 if the bone marrow test is considered noncontributory by the investigator at any time point.

7.2.6 Concomitant medication data will not be collected or entered into the case report form except for concomitant hydroxyurea; however, the subject's medication record will contain a list of concomitant medications.

Correlative Studies relating to immunologic response (Optional):

Tumor tissue, blood samples and bone marrow aspirate will be collected from patients under Z20160444 and will be sent to [name] lab at MD Anderson for research

purposes (described below). Patients will be consented separately on this IRB approved consent for collection of additional material. Correlative laboratory studies will be conducted under this clinical trial protocol as described below.

7.2.7 Patients may participate in the clinical study protocol irrespective of whether they choose to participate in the correlative studies. In tumor tissues, immunohistochemical studies will be performed to evaluate tumor and immunological cell markers such as CD4 and CD8 T cells. In peripheral blood, we will also evaluate tumor and immune cell populations including but not limited to CD4 and CD8 T cells in pre and post therapy samples.

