All patients who received any dose of the study agent will be included in the analysis for efficacy and safety. Demographic/clinical characteristics (including duration of response) and safety data of the patients will be summarized using descriptive statistics such as mean, standard deviation, median and range. For the primary efficacy analysis, we will estimate the ORR for the combination treatment, along with the 95% credible interval. For the efficacy, a sample size of 40 patients ensures a posterior 95% credible interval for ORR of (0.17, 0.43), if the trial is not terminated early, under the assumption of a 30% ORR. Patients who drop out of the study before completing all the cycles will be treated as “failures” for the primary analysis. ORR during the study period will also be presented with the 95% confidence credible. The association between ORR and patient’s clinical characteristics will be examined by Wilcoxon’s rank sum test or Fisher’s exact test, as appropriate. Toxicity type, severity and attribution will be summarized for each patient using frequency tables.

The distribution of time-to-event endpoints (DFS and OS) including overall survival and progression free survival will be estimated using the method of Kaplan and Meier. Comparisons of time-to-event endpoints by important subgroups will be made using the log-rank tests. Paired t-tests will be used to determine the immunological and molecular changes in the peripheral blood and bone marrow from baseline to the time of response, and to the time of disease progression. Correlation analysis (such as logistic regression analysis) will be conducted to determine the relationship between induction of hypomethylation / DNA damage and clinical response.

A Toxicity Summary will be submitted to the IND Office Medical Monitor, after the first three patients have completed their first cycle of study therapy or administration is

discontinued, whichever comes first, and every three evaluable patients thereafter during the Lead-in Phase IB.

An Efficacy/Toxicity Summary will be submitted every five evaluable patients during **Phase II**.

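### Systemic steroid use is kept off the CRF, so the planned pre/post T-cell analyses cannot identify samples drawn on steroids

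*Combined protocol and SAP*

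**What the plan says.** **Objective.** Section 1.4, exploratory objective 1, sets out to "determine the quantitative expression of positive and negative co-stimulatory molecules on individual T-lymphocyte subsets" and to phenotype marrow T cells before and after therapy.

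**Steroid use.** On patients already enrolled, section 5.6 says: "They may receive systemic, topical, inhaled, or enteric corticosteroids while on study without limitation if they develop conditions that require corticosteroid therapy". They need not leave the study. Table 3 (section 5.3.5) prescribes methylprednisolone for many immune-related events, at 0.5 to 4 mg/kg/day depending on the row. Tapers last at least one month, or at least six weeks for grade 3–4 pneumonitis. Section 4.2.7 also admits some post-transplant patients on systemic steroids or on a stable calcineurin inhibitor.

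**Data capture.** Section 5.6: "Concomitant medication data will not be collected or entered into the case report form other than hydroxyurea as mentioned above". Section 7.2.6 repeats the rule: "Concomitant medication data will not be collected or entered into the case report form except for concomitant hydroxyurea". Both add that the subject's medication record will list concomitant drugs. Section 7.2.1 and Table 6 call for these drugs to be documented at the start of each cycle.

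**Analysis.** Section 11.2, under its Statistical Analysis Plan heading: "Paired t-tests will be used to determine the immunological and molecular changes in the peripheral blood and bone marrow", from baseline to response and from baseline to progression. The biomarker paragraph that follows adds pairwise comparisons of each patient's pre- and post-therapy samples. Neither place names a steroid covariate, a flag, an exclusion or a sensitivity analysis.

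**The concern.** The trial has one arm, so each marker change is judged only against the patient's own baseline. Whatever else changes between the two samples is absorbed into the apparent drug effect. Steroids for immune-related events start after baseline and so load onto the later sample of the pair.

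The protocol itself treats these drugs as relevant to immunity. Section 5.2.1 bars systemic corticosteroids from avelumab premedication, and Table 3 describes the step beyond steroids for pneumonitis as further immunosuppression. The correlative section (7.2) hopes these data will yield prognostic and predictive markers and point to other checkpoints for future trials. A change produced by a steroid course could be read as an effect of avelumab plus azacytidine, and the CRF data set would give the analyst no means of noticing.

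This is more than a missing detail. The protocol states twice, as a rule, that the information will not be collected on the CRF, while making an exception for one other drug.

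**Working it through.** **1. Can steroid exposure coincide with sampling?** Section 7.2.7 schedules correlative blood at baseline, at days 14 and 28 of cycle 1, during cycle 2, and at days 1 and 14 of cycles 4, 8 and 12. Marrow is taken at baseline, at day 28, and at day 28 of later cycles. A cycle is 28 days. A steroid course that starts on study day 15 and lasts one month runs past study day 43. It covers the day 28 sample and day 14 of cycle 2 (28 + 14 = study day 42). Several Table 3 rows (grade 2 diarrhoea, pneumonitis and liver tests; rash; endocrine) allow avelumab to resume, and section 5.3.4 allows interruptions for prolonged tapers while leukemia assessments continue. Exposed patients can therefore still supply samples.

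**2. Can the CRF data identify those samples?** No. Hydroxyurea is the only concomitant drug captured. Adverse events are recorded (section 7), but an event entry gives neither steroid dose nor dates. Scheduled medication documentation falls on day 1 of each cycle (±4 days), whereas many correlative samples fall on days 14 and 28.

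**3. How many pairs?** The documents give no number of pairs, alpha, power or SD for these analyses, so there is no plan figure to reproduce. The t-tests run to response and to progression. At the target ORR, response pairs number 0.30 × 40 = 12 in phase II, or 0.30 × 52 to 0.30 × 58 = about 16 to 17 over total accrual. All correlative samples are optional, so these are upper figures at that ORR. Only the general pre/post comparison could approach 40 pairs.

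**4. Illustration.** Inputs, all assumed: no study-drug effect; paired differences with SD 1; a share f of post-therapy samples drawn on steroids; a shift of d SD in each of those.

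- Bias in the mean change = f × d. For d = 1 and f = 0.20 this is 0.20 SD.
- Approximate noncentrality = f·d·√n / √(1 + d²·f(1 − f)). For n = 40, f = 0.20, d = 1: 0.20 × 6.325 / √1.16 = 1.17. The normal approximation gives a rejection rate near 0.22, and simulation of the t-test gives 0.21.

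Simulated rejection rates for a two-sided 5% paired t-test:

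| Pairs | d | f = 10% | f = 20% | f = 30% |
|---|---|---|---|---|
| 12 | 1.0 | 6% | 9% | 13% |
| 20 | 1.0 | 7% | 12% | 21% |
| 40 | 1.0 | 9% | 21% | 39% |
| 12 | 0.5 | 5% | 6% | 8% |
| 20 | 0.5 | 6% | 7% | 9% |
| 40 | 0.5 | 6% | 9% | 15% |

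At f = 5% every setting stays at or below 6%. The test is two-sided, so the direction of the shift does not affect these rates.

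**The case against.** **The information is not lost.** The medication record lists concomitant drugs, they are documented each cycle, and all avelumab is given at one centre. Nothing restricts the biomarker analysis to CRF fields. This stands. A reader might infer that steroid effects can never be examined; the documents do not support that. What is missing is a planned step to link steroid dose and dates to sampling dates.

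**The larger error rates need favourable inputs.** A reader might take 21–39% as the plan's error rate. Those figures need 40 pairs and a full 1 SD shift, whereas the baseline-to-response test would have about 12 pairs at 30% ORR. The documents give neither f nor d, nor the direction in which steroids move any particular marker. This stands too.

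**Exposure is limited in places.** The grade 3–4 colitis, pneumonitis and liver rows of Table 3 discontinue avelumab, and cycle 1 leaves little time for immune-related events to be treated before sampling. That lowers f but does not make it zero.

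**Stable transplant immunosuppression.** A reader might count tacrolimus or cyclosporine at entry as a further source of bias. Section 4.2.7 requires a stable dose, so the drug is largely present in both samples and mostly cancels in the difference. Only a change after baseline matters. Baseline steroids tapered later would push the bias the other way.

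**Restricting the main analysis to low-steroid samples would be wrong.** Steroid use follows immune-related events that may themselves reflect drug effect, so such a restriction conditions on a post-treatment event. Nor is the 10 mg prednisone limit an on-study threshold: in sections 4.2.5 and 5.6 it concerns hormone replacement or use at enrollment. Section 4.2.7 admits post-transplant patients on prednisone below 1 mg/kg, so the baseline steroid passages need reconciling in any case. This objection stands and shapes the fix.

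**Conclusion.** The point holds as a data-capture gap. On-study systemic steroids are foreseen and uncapped when a condition requires them, the CRF excludes them by rule, and the single-arm pre/post analyses have no variable with which to flag exposed samples.

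The size cannot be derived from the documents. Under the stated assumptions (no drug effect, 10–30% of post-therapy samples exposed), a nominal 5% test rejects in about 6–13% of cases with 12 pairs and up to 39% with 40 pairs for a 1 SD shift, and in about 5–15% for 0.5 SD. If few samples are drawn on steroids the problem is negligible; the CRF as planned cannot show which case applies.

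The consequence is confined to exploratory objective 1. A reader might infer that the trial's main conclusions are at risk; they are not, since MTD, ORR and the stopping rules do not use these data. This is a cheap improvement worth making, not a flaw in the primary design.

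**What to change.** 1. In sections 5.6 and 7.2.6, add systemic corticosteroids and other systemic immunosuppressants (agent, dose, start and stop dates) to hydroxyurea as CRF items. Cover at least the period around each correlative sample, including baseline. The entries can be transcribed from the medication record already required.
2. In section 11.2, keep the all-sample paired analysis as the main analysis. Flag pairs in which systemic steroid or immunosuppressant exposure differs between the two samples, and pre-specify a sensitivity analysis without them.
3. State that this sensitivity analysis conditions on a post-treatment event. It shows whether a finding depends on steroid-exposed samples but cannot fully separate steroid from study-drug effects without a control arm.

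The cost is a few CRF fields, a short addition to the analysis text, and fewer pairs in the sensitivity analysis. No treatment rule changes.
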